2.0 STUDY ENDPOINTS AND OBJECTIVES

2.1 Primary Objective

1. To determine the percent weight loss in patients during POAmCRT (Arm 1) starting at Day 1 and ending on the last day of RT.

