5.10 Duration of Therapy

If at any time the constraints of this protocol are considered to be detrimental to the patient’s health and/or the patient no longer wishes to continue protocol therapy, the protocol therapy should be discontinued and the reason(s) for discontinuation documented in the case report forms.

In the absence of treatment delays due to adverse events, treatment may continue for the duration of surgery and RT +/- cisplatin until one of the following criteria applies:

- Documented and confirmed disease progression
- Death
- Adverse event(s) that, in the judgment of the investigator, may cause severe or permanent harm or which rule out continuation of study drug
- General or specific changes in the patient's condition render the patient unacceptable for further treatment in the judgment of the investigator
- Suspected pregnancy
- Serious non-compliance with the study protocol
- Lost to follow-up
- Patient withdraws consent
- Investigator removes the patient from study
- The Siteman Cancer Center decides to close the study

Patients who prematurely discontinue treatment for any reason will be followed as indicated in the study calendar.

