7.2 Radiation Dose Modifications

There are no planned dose modifications or delays for radiation therapy. Delays are allowed at the discretion of the treating physician.

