10.2 Sample Size Calculation

The primary endpoint is percent weight loss from Day 1 of treatment to last day of RT. The sample size calculation is based on the primary endpoint only. Our historical data showed that the mean and standard deviation of percent weight loss during POACRT in patients with HPV-related OPSCC are 7.39% and 5.46%, respectively. The primary hypothesis of this trial is that the percent weight loss of patients in Arm 1 during POAmCRT will be 3.7% (50% reduction). Twenty patients

will have 80% power to detect the percent weight loss difference if assuming the standard deviation of 5.46% using a two-sided one-group t test at the type I error of 5%. We will enroll 24 patients in Arm 1 accounting for 15% drop-out²². We estimate that 14 patients will be enrolled in Arm 2 and 6 patients will be enrolled in Arm 3 for a total of 40 patients.

In December 2019, we reached the 40 patient enrollment mark. However, Arm 1 had enrolled only 13 of the target of 20 patients at that time. In June 2020, we plan to increase enrollment to reach 7 additional patients on Arm 1, or 20 additional patients onto any arm, whichever comes first.

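### Weight loss after an early, toxicity-driven stop of RT does not enter the primary endpoint, which tends to understate the Arm 1 mean modestly

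*Combined protocol and SAP*

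**What the plan says.** - **Window.** Section 2.1 measures loss in Arm 1 "starting at Day 1 and ending on the last day of RT". Section 10.2 repeats this: "The primary endpoint is percent weight loss from Day 1 of treatment to last day of RT". Neither says whether the actual or the planned last day is meant.
- **Early stopping.** Section 5.10 lists among the reasons for ending treatment "Adverse event(s) that, in the judgment of the investigator, may cause severe or permanent harm or which rule out continuation of study drug". It adds: "Patients who prematurely discontinue treatment for any reason will be followed as indicated in the study calendar". Section 5.7 makes everyone who receives any post-operative RT evaluable for toxicity.
- **Delays.** Section 7.2 plans no RT modifications but says "Delays are allowed at the discretion of the treating physician".
- **Weights.** Sections 5.4.1 and 10.4.4 collect weight weekly during radiation. The calendar in 14.1 marks a weight at day 36, but its footnote again refers to weekly weights during radiation. The first clearly scheduled weight off treatment is at the six-week follow-up visit (5.6.1).
- **Analysis.** Section 10.2 sizes the trial on a one-group t test against a historical 7.39%. Section 10.4.4 instead models weekly percent loss by time point with a GEE. It gives no rule for missing weeks and no comparison with 7.39%.

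**The concern.** Section 1.9 uses weight loss as the surrogate for mucosal toxicity, and the case for de-intensified treatment rests on it. Toxicity severe enough to end RT also ends the weekly weighing and, on the ordinary reading, closes the measurement window. Such a patient's loss is then measured over a shorter period than that of patients who complete, for a reason tied to the outcome itself. What happens to weight between the stop and the planned end never reaches the primary endpoint.

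This matters because the missing part is probably further loss. The error therefore tends to favour the hypothesis of a halved mean. It also cannot be repaired afterwards: a weight not taken near the planned end of RT cannot be recovered at the six-week visit.

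**Working it through.** **1. The plan's own figure.** Inputs from Section 10.2: "standard deviation of percent weight loss during POACRT in patients with HPV-related OPSCC are 7.39% and 5.46%, respectively" (the first figure is the mean), an Arm 1 target of 3.7%, and a two-sided one-group t test at 5%.

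- Difference = 7.39 − 3.7 = 3.69 points.
- Power from the non-central t: 81.8% at n = 20 and 79.5% at n = 19. So 20 is the smallest n that reaches 80%.
- Allowing for drop-out: 20 / 0.85 = 23.5, rounded up to 24.

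Both of the plan's figures reproduce.

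**2. What a favourable result needs.** At n = 20 the critical t is 2.093, so the observed mean must be at or below 7.39 − 2.093 × 5.46/√20 = 4.83%, which is 2.56 points under the historical mean.

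**3. Effect of truncation on the t test.** The documents give no rate of early stopping and no shape for the loss over time. Assume linear loss, a constant SD of 5.46%, a true full-course mean m = 7.39% (no benefit), and k of 20 patients stopping after a fraction t of the course while losing at r times the average rate.

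- Recorded loss of a stopper = r × t × m.
- Understatement of the mean = (k/20) × r × (1 − t) × m.

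For average-rate stoppers (r = 1):

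| k | t | Understatement (points) | Recorded mean | False favourable rate |
|---|---|---|---|---|
| 0 | – | 0 | 7.39% | 2.5% |
| 1 | 0.5 | 1/20 × 0.5 × 7.39 = 0.18 | 7.21% | 3.5% |
| 2 | 0.5 | 2/20 × 0.5 × 7.39 = 0.37 | 7.02% | 4.7% |
| 3 | 0.5 | 3/20 × 0.5 × 7.39 = 0.55 | 6.84% | 6.3% |
| 3 | 0.25 | 3/20 × 0.75 × 7.39 = 0.83 | 6.56% | 9.5% |

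Rates come from the non-central t with 19 degrees of freedom. Simulation with the stoppers' values scaled down gives 3.5%, 4.7%, 6.5% and 9.0% for the four rows with stoppers.

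**4. Fast losers.** With r = 2 and t = 0.5, a stopper is recorded at 2 × 0.5 × 7.39 = 7.39%, exactly the average. The true mean would be 7.39 × (1 + k/20) = 7.76%, 8.13% or 8.50% for k = 1, 2 or 3. The recorded mean stays at 7.39%, so the understatement is 0.37, 0.74 or 1.11 points. With the SD held fixed, the false favourable rate stays at 2.5%.

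**5. The GEE.** Here an early stopper contributes true values while on RT and then has missing weeks. As an illustration, 20 patients were simulated over weeks 1 to 4 with an AR(1) working correlation and baseline weight in the model. When the three fastest losers stopped after week 2, the week-4 estimate averaged about 6.5%, against 7.4% with everyone weighed: about 0.9 points low. When the stoppers are average losers, the bias is small. The documents fix neither the size nor the direction.

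**The case against.** Much of the case on the other side stands.

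- **The window is ambiguous.** Sections 2.1 and 10.2 do not say actual or planned last day. Reading it as the patient's own last day is natural, but it is a reading. What stands without it is that no weight is clearly scheduled at the planned end for someone who has stopped.
- **The analysis section has no single end value.** Under the GEE, no small final value is entered for a stopper. The problem becomes toxicity-related missingness, which does not remove it.
- **Success is not counted per patient.** A reader might infer that an early stopper scores as a success. The endpoint is a mean, and no patient is classified.
- **Stoppers need not be among the smallest losses.** A stopper is recorded below average only if r × t is under 1. The double-rate case above is recorded exactly at average. It is safe to say only that the value is probably lower than the same patient would have shown at the planned end.
- **The 15% drop-out is not a benchmark for stoppers.** It is a reader's tempting source for three in 20, but drop-outs already lie outside the 20 evaluable patients.
- **Delays do not shorten the window.** Those allowed by Section 7.2 lengthen it and would tend to record more loss, against Arm 1.
- **The comparator may share the problem.** The documents do not say how the historical window was closed. If it also ended at the actual last day, part of the bias could cancel.
- **The effect is small** against the 2.56 points needed for significance.

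**Conclusion.** The concern holds in a limited form. The plan ties the primary window and the weighing schedule to the time on RT, permits toxicity to end RT, and has no rule for the weights of patients who stop. This tends to understate the Arm 1 mean.

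Under average-rate, mid-course stopping of one to three in 20, the understatement is 0.18 to 0.55 points and the false favourable rate is 3.5% to 6.3% instead of 2.5%. Those figures assume linear loss, a constant SD of 5.46% and the t test of Section 10.2. Early stopping alone would carry an expected mean of 7.39% to the 4.83% threshold only if about 35% of all loss went unrecorded (2.56/7.39), for example 7 of 20 patients recorded at zero. The documents do not support reading this as a flaw that could by itself produce the hoped-for result. It is worth correcting because the correction is cheap and the lost weights cannot be recovered later. Where the window of a completed course ends, relative to the longer historical treatment, is a separate question.

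**What to change.** Amend Sections 5.4.1, 10.2 and 10.4.4, and bring the weight footnote in the 14.1 calendar into line:

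1. For every Arm 1 patient who starts RT and stops before fraction 21, continue the weekly weights to the date on which fraction 21 was scheduled in that patient's own RT plan. Use that last weight as the end-of-RT value, and all of these weights in the GEE.
2. For patients who complete RT, including after delays, keep the actual last day of RT. Closing their window on the planned day would cut off loss that occurs during treatment.
3. Report the actual-last-RT-day value for all patients as a sensitivity analysis, since the historical 7.39% may have been measured that way.

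The date should come from the individual plan because the documents do not give one planned length. Section 5.5 has one twice-daily treatment per course or none, Section 5.5.8 gives 4 to 4 1/5 weeks, and the calendar footnote has one twice-daily treatment each week. Those passages need to be reconciled in any case.

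The cost is a sentence or two in each section and a few extra weights from patients whom Section 5.10 already keeps in follow-up. The observed mean loss may come out slightly larger. Only measurement changes, not treatment.

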2.2 Secondary Objectives

1. To evaluate the narcotics administration of patients 6 weeks after POAmCRT (Arm 1).
2. To determine the disease recurrence rate at 24 months post-treatment in each arm.

3. To determine progression free survival (PFS) and overall survival (OS) for each arm.
4. To evaluate the proportion of PEG tube placements in each arm.
5. To determine the serum creatinine changes in patients receiving POAmCRT (Arm 1).

2.3 Exploratory Objectives

1. To document the measures of Quality of Life (QOL) at baseline, during treatment, and through one year after completion of treatment in each arm.

3.0 PATIENT ELIGIBILITY

3.1 Inclusion Criteria

1. Histologically or cytologically confirmed HPV-related stages I-III OPSCC (8th edition of AJCC/UICC Staging Manual) or HPV-related neck node with unknown primary. HPV-related may be defined by p16 IHC stain and/or HPV-ISH or PCR using standard definitions of positive and negative test results. cT1N0 and cT2N0 excluded.
2. Primary tumor that will be resected via a transoral oral approach (conventional surgery, transoral laser microsurgery, transoral robotic surgery)
3. ECOG PS 0-2.
4. Normal organ and marrow function defined as:
 - a. Creatinine clearance > 50 cc/min.
 - b. ANC \geq 1,000/mcL.
 - c. Platelet count \geq 100,000/mcL.
5. At least 18 years of age.
6. Women of childbearing potential and men must agree to use adequate contraception (hormonal or barrier method of birth control, abstinence) prior to study entry and for the duration of participation. Should a woman become pregnant or suspect she is pregnant while participating in this study, she must inform her treating physician immediately.
7. Patient (or legally authorized representative) must be able to understand and willing to sign a written informed consent document.

3.2 Exclusion Criteria

1. cT1N0 or cT2N0 staging.
2. Prior curative therapy for HNSCC.
3. Patient must not have known distant metastatic disease at presentation.
4. History of prior invasive malignancy diagnosed within 2 years prior to study enrollment; exceptions are malignancies with a low risk of metastasis or death (e.g., expected 5-year OS > 90%) that were treated with an expected curative outcome, such as squamous cell carcinoma of the skin, in-situ carcinoma of

- the cervix uteri, non-melanomatous skin cancer, carcinoma in situ of the breast, or incidental histological finding of prostate cancer (TNM stage of T1a or T1b).
- 5. Receiving any other investigational agents.
- 6. Uncontrolled serious inter-current illness or serious psychiatric illness/social situations that would limit compliance with study requirements.
- 7. Pregnant and/or breastfeeding. A negative serum or urine pregnancy test is required at screening for all female patients of childbearing potential.

3.3 Inclusion of Women and Minorities

Both men and women and members of all races and ethnic groups are eligible for this trial.

4.0 REGISTRATION PROCEDURES

Patients must not start any protocol intervention prior to registration through the Siteman Cancer Center.

The following steps must be taken before registering patients to this study:

1. Confirmation of patient eligibility
2. Registration of patient in the Siteman Cancer Center OnCore database
3. Assignment of unique patient number (UPN)

4.1 Confirmation of Patient Eligibility

Confirm patient eligibility by collecting the information listed below:

1. Registering MD's name
2. Patient's race, sex, and DOB
3. Three letters (or two letters and a dash) for the patient's initials
4. Copy of signed consent form
5. Completed eligibility checklist, signed and dated by a member of the study team
6. Copy of appropriate source documentation confirming patient eligibility

4.2 Patient Registration in the Siteman Cancer Center OnCore Database

All patients must be registered through the Siteman Cancer Center OnCore database.

4.3 Assignment of UPN

Each patient will be identified with a unique patient number (UPN) for this study. All data will be recorded with this identification number on the appropriate CRFs.

5.0 TREATMENT PLAN AND SCHEDULED ASSESSMENTS

Patients with HPV-related OPSCC will undergo resection of the primary tumor site and involved/at risk regional neck nodes. Based on the clinical and pathologic staging and the details of the pathology report, patients will be assigned to one of three adjuvant treatments. Arm 1 (ECE or positive margin but not clinical or pathologic T4 or clinical N3 disease) will be treated with POAmCRT (42 Gy RT + cisplatin 1 dose). Arm 2 (no ECE, no positive margins, and not clinical or pathologic T4 or clinical N3 disease) will be treated with POAmRT (42 Gy RT, no cisplatin). Arm 3 (clinical or pathologic T4 or clinical N3 disease) will be treated with POART (60 Gy RT). If there is pathologic evidence of ECE or positive margin, 3 cycles of cisplatin will be given concurrently with POART (60Gy).

Please note that because weight loss is the primary endpoint, a specific scale must be chosen at each facility. It is the responsibility of the research coordinator to ensure that the same scale is used for all patients at that facility. Patient weight will be assessed with clothes on (no outer layers such as jackets) and shoes off.

5.1 Baseline Assessment

The baseline assessment will include the following tests or procedures and must occur within 35 days (PET scan within 42 days) of enrollment:

1. Clinical examination to document extent of primary tumor by laryngoscopy performed in the office or in the operating room (depending on the ease of the exam and the primary tumor site) and palpable involved regional neck nodes.
2. Documentation of site of primary tumor (HPV-related oropharynx or CUP), location and level of clinically involved neck nodes (right or left neck, Level I-V), T stage (1-4), N stage (0-3), and overall clinical stage (I-III by AJCC Cancer Staging Manual Eighth Edition).
3. Documentation of demographic information, including gender (M/F), age (years), height (cm), weight (Kg), and BSA (m²).
4. Documentation of baseline patient symptoms using NCI-CTCAE version 4.0.
5. Documentation of ECOG performance status (Appendix 1).
6. Completion of QOL questionnaires (Appendices 3, 4, 5, 6, and 7).
7. Documentation of Comorbidity Index (Appendix 2).
8. Laboratory evaluations: CBC, CMP, magnesium, PT/PTT, serum pregnancy test if patient is a female of childbearing potential.
9. CT scan of the neck (IV contrast preferred) to document and measure the extent of the primary tumor size and involved regional neck nodes.
10. FDG-PET/CT scan (whole body) to document and measure the FDG avidity at the primary tumor site and at the involved regional neck nodes.
11. OPTIONAL: Speech and swallowing assessment including a modified barium swallow (MBS) study and the Performance Status Scale for Head and Neck Cancer (PSS-HN) questionnaire (Appendix 8).

5.2 Standard of Care Surgery

Patients will undergo a typical preoperative workup in preparation for surgery, including routine lab work, electrocardiogram, and a preoperative assessment by anesthesiology. Patients will undergo surgical resection of the primary tumor via a transoral approach, including conventional transoral surgery, transoral laser microsurgery (TLM), or transoral robotic surgery (TORS). The choice of surgical technique will be based on surgeon preference, tumor characteristics, and tumor site. Margin status will be assessed intra-operatively on frozen section and confirmed on permanent section.

At the time of transoral resection, patients will also undergo surgical management of cervical lymph nodes via a conventional selective neck dissection. For oropharyngeal tumors, this most often includes dissection of Levels II-IV. If the tumor approaches within one centimeter of midline, the patient will undergo bilateral neck dissections.

The pathology report documents margin status, perineural invasion, lymphovascular invasion, and extracapsular extension (ECE). Margins will be considered positive if gross or microscopic disease is present at the margins based on the surgical pathologist's judgement. ECE will be defined as tumor extending beyond the lymph node capsule into the surrounding soft tissue (AJCC 8th Edition Staging Manual). ECE will be measured when possible; however, extensive ECE or soft tissue metastases may preclude this measurement.

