and thus all patients are treated with adjuvant therapy to reduce the risk of disease recurrence. The standard radiation dose used in this setting is 60 Gy, and most of these patients also receive concurrent cisplatin 100 mg/m²/dose for up to three doses. Based on studies in anal SCC, 42 Gy of RT should eliminate microscopic disease in most patients with OPSCC who have undergone complete resection of all gross disease. Studies in anal SCC used a total cisplatin dose of 150 mg/m²; however, these patients were managed non-operatively and thus all patients had gross disease when CRT was initiated. For this reason, a total dose of cisplatin lower than 150 mg/m² seems reasonable to explore in patients with OPSCC who have undergone complete resection of all gross disease. In HNSCC, 5-FU has not been shown to add benefit to RT.

De-intensification of adjuvant therapy by reduction in radiation dose from 60 Gy to 42 Gy and in the total cisplatin dose from 300 to 100 mg/m² should result in a substantial reduction in acute toxicity and improvement in QOL, but this is only acceptable if there is not an increased risk of disease relapse.

1.9 “The **MINT** Trial”

The overarching goal of the **MINT** trial is to reduce treatment-related toxicity while maintaining efficacy. Patients with HPV-related OPSCC will undergo resection of the primary tumor site and involved/at risk regional neck nodes. Based on the clinical and pathologic staging and the details of the pathology report, patients will be assigned to one of three adjuvant treatments:

- **Arm 1** (extracapsular extension (ECE) or positive margin but not clinical or pathologic T4 or clinical N3 disease) will be treated with POAmCRT (42 Gy RT + cisplatin 1 dose)
- **Arm 2** (no ECE, no positive margins, and not clinical or pathologic T4 or clinical N3 disease) will be treated with POAmRT (42 Gy RT, no cisplatin)
- **Arm 3** (clinical or pathologic T4 or clinical N3 disease) will be treated with POART (60 Gy RT). If there is pathologic evidence of ECE or positive margin, 3 cycles of cisplatin will be given concurrently with POART (60Gy).

Intermediate risk patients will be assigned to Arm 1 where they will be treated with de-intensified CRT: 42 Gy of RT (vs 60 Gy) and cisplatin 1 dose (vs 3). Reduction in treatment-related toxicity is expected in Arm 1.

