5.3 Interim Assessment

The interim assessment will include the following tests or procedures and should occur within 14-42 days of surgery:

1. Clinical examination.
2. Documentation of key data from the pathology report: T (1-4) and N (0-3) stage, ECE status (+/-) and extent of ECE (mm), margin status (+/-).
3. Arm assignment (based on pathology data)
4. Documentation of patient symptoms using NCI-CTCAE version 4.0; please note that AEs considered at least possibly related to surgery need not be recorded.
5. Documentation of ECOG performance status.
6. Completion of QOL questionnaires.
7. Documentation of Comorbidity Index.
8. Laboratory evaluations: CBC, BMP, magnesium, PT/PTT.
9. OPTIONAL: Speech and swallowing assessment including MBS and PSS-HN questionnaire.

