5.5.2 Virtual Simulation and Contouring

The CT scan will be exported to a commercially available virtual simulation software package. Guidelines for delineating each lymph node level will be based on the international consensus for delineation of head and neck lymph nodes (<http://www.rtoq.org/hnatlas/main.html>). These guidelines were derived in part from Washington University School of Medicine institutional data and are consistent with routine clinical practice at Washington University.

Arms 1 and 2: An example case of a T3N2BM0 (AJCC 7th edition), stage IVA tonsil cancer is outlined in the table below. Current treatment guidelines for this case including dose levels are represented with CTV1 and CTV2.

CTV1	CTV2
[GTVp + GTVn] + 1.0 to 1.5 cm minimum concentric margin excluding bone and air with aid of preop imaging with/without fusion	IN (II-V) + BRPLN + CN (IIb-IV) Exclusive of CTV1.
Dose 42 Gy/21 fx	Dose 37.8 Gy/21 fx

Key: GTVp = GTV primary tumor; GTVn = GTV nodal tumor; IN = ipsilateral neck; CN = contralateral neck; roman numbers relate to the level system of naming lymph node regions; BRPLN = bilateral retropharyngeal lymph nodes).

Arm 3: An example case of a T4N2M0 (AJCC 7th edition), stage IVA tonsil cancer is outlined in the table below. Current treatment guidelines for this case including dose levels are represented with CTV1 and CTV2.

CTV1	CTV2
[GTVp + GTVn] + 1.0 to 1.5 cm minimum concentric margin excluding bone and air with aid of preop imaging with/without fusion	IN (II-V) + BRPLN + CN (IIb-IV) Exclusive of CTV1.
Dose 60 Gy/30 fx	Dose 52 Gy/30 fx

Key: GTVp = GTV primary tumor; GTVn = GTV nodal tumor; IN = ipsilateral neck; CN = contralateral neck; roman numbers relate to the level system of naming lymph node regions; BRPLN = bilateral retropharyngeal lymph nodes).

Normal structure and treatment volume contours will be delineated in a manner consistent with routine clinical practice.

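### The Arm 1 rule admits gross positive margins, although section 1.8 supports 42 Gy plus one cisplatin dose only when all gross disease has been resected

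*Combined protocol and SAP*

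**What the plan says.** Section 5.2 defines margin status: "Margins will be considered positive if gross or microscopic disease is present at the margins", as the surgical pathologist judges. Gross and microscopic involvement carry the same label.

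Section 5.0 turns that label into treatment: "Arm 1 (ECE or positive margin but not clinical or pathologic T4 or clinical N3 disease) will be treated with POAmCRT". Section 1.9 gives the same rule. Section 5.5 sets the Arm 1 dose to the post-operative tumour bed at 4200 cGy in 21 fractions, and 5.4.1 adds a single cisplatin dose of 100 mg/m². The 60 Gy regimen of Arm 3 is triggered only by T4 or cN3.

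Section 5.3 lists what is taken from the pathology report before the arm is chosen: "ECE status (+/-) and extent of ECE (mm), margin status". Margin is recorded only as plus or minus.

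The rationale in section 1.8 is narrower. On dose it says: "42 Gy of RT should eliminate microscopic disease in most patients with OPSCC who have undergone complete resection of all gross disease". On cisplatin it argues that a total below the 150 mg/m² of the anal cancer regimen is reasonable because, in the anal studies, "these patients were managed non-operatively and thus all patients had gross disease when CRT was initiated", whereas here the gross tumour has been taken out.

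**The concern.** The argument for less radiation and less cisplatin depends on there being only microscopic disease left. The rule that assigns patients to the reduced regimen does not carry that condition. Read literally, it would give a patient who is known to have gross tumour left after surgery 42 Gy and one cisplatin dose, which is outside the protocol's own justification. The cancer is curable, and section 1.8 itself accepts de-intensification only if relapse does not rise. What is at stake is the safety of an individual patient. The weight-loss comparison is not touched.

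**Working it through.** The point rests on the text, so the check is to follow one patient through the rules and then look for anything that diverts that patient.

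**Following the rule.** Take a patient without T4 or cN3 who has gross disease at the final margin.

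1. By 5.2 the margin is positive.
2. By 5.3 the record shows plus, the same as for a microscopic margin.
3. By 1.9 and 5.0 the arm is Arm 1. Arm 2 requires a negative margin, and Arm 3 requires T4 or cN3.
4. By 5.5 and 5.4.1 the treatment is 21 × 2 Gy = 42 Gy to the tumour bed plus 100 mg/m² of cisplatin.
5. By 1.8 that treatment is argued for only where gross disease has been fully removed. If this patient still has gross tumour, steps 3 and 5 conflict.

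**Looking for a rule that diverts the patient.**

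- Eligibility (3.1, 3.2) is settled before surgery. It asks that a transoral resection is planned, not that it succeeds in clearing gross tumour.
- Section 1.4 gives removal of all gross disease as the goal of surgery. It is not a condition of assignment.
- Section 5.2 requires frozen-section assessment with permanent-section confirmation. It does not say whether the margin used for assignment is the one after any further resection.
- The interim examination (5.3), the planning CT (5.5.1) and the physician's plan review (5.5.7) could reveal residual tumour. None says what then follows.
- Section 5.10 says protocol therapy should stop if its constraints are considered harmful to the patient, and it lets the investigator remove a patient. This is the only route out. It depends on judgement and does not name gross residual disease.

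**Reach.** Section 10.2 reports 13 of 20 Arm 1 patients enrolled by December 2019, and 20 − 13 = 7 more were sought. A wording change can affect at most those 7. The documents give no rate of gross margins or of gross residual disease, so no expected number can be calculated.

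**Sample size.** The plan's figures reproduce. The difference is 7.39 − 3.7 = 3.69 points, and 3.69/5.46 = 0.676 SD. A two-sided one-sample t test at 5% has power 0.818 with 20 patients. For drop-out, 20/(1 − 0.15) = 23.5, rounded up to 24. None of these inputs depends on how a gross margin is handled. If one patient left Arm 1 and was not replaced, power with 19 would be 0.796.

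**The case against.** The strongest reply is that the margin sentence in 5.2 tells a pathologist how to read a specimen and does not describe a patient left with tumour. Gross disease at a specimen edge may be cleared by further resection. The whole protocol is set in the adjuvant treatment of microscopic disease (1.4, 1.8), and 5.10 already allows, and in its wording directs, that harmful protocol therapy be stopped. On this view the fix only spells out what an investigator would do anyway.

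Much of this stands. A gross specimen margin is not the same as known gross residual disease, and the surgical aim and frozen-section control make the case uncommon. What remains is that the text does not separate the two situations, and that a stated rule points the wrong way unless someone overrides it.

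Two other passages look like support but add little. The planning table in 5.5.2 ("Dose 42 Gy/21 fx") is one example case, so the absence of a boost level there proves little. Section 7.2 ("There are no planned dose modifications or delays for radiation therapy") sits under the management of adverse events and is not about residual tumour. Section 5.5 carries the dose point.

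A reader might also infer a measured under-dose from section 1.8, where gross anal tumour receives 50.4 to 54 Gy, which is 8.4 to 12 Gy above 42 Gy. The documents do not support that inference. The comparison is with unresected tumour at another site under a different regimen, and no dose is settled for gross residual oropharyngeal disease.

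**Conclusion.** The concern holds as a mismatch between rule and rationale: Arm 1 is defined more broadly than the case made for its treatment, and only discretion under 5.10 fills the gap. It is a minor safety wording change.

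A reader might infer that patients with known gross tumour have been, or will be, under-treated in Arm 1. The documents do not show this. They describe no such patient and give no frequency, and the number affected among the 7 further patients may be zero. Nor does the point weaken the primary analysis.

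The conclusion assumes that sections 1.9, 5.0 and 5.2 are applied as written, and that section 1.8 is meant to limit the regimen to patients without gross disease, as its wording indicates.

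**What to change.** - In 1.9 and 5.0, add to the Arm 1 definition: *and no known gross residual disease after final resection*. Because the clause refers to residual disease, a gross specimen margin cleared by further resection stays in Arm 1.
- In 5.2, state that margin status is the final status after any further resection.
- In 5.3, record gross or microscopic beside the plus or minus.
- State that a patient with gross residual disease that cannot be re-resected does not receive 42 Gy, stops protocol therapy under 5.10, is treated at the investigator's choice, and is followed as 5.10 already provides.

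The cost is wording in four sections and one item from the existing pathology report, with no new visits or tests. The downside is that a rare patient leaves Arm 1 and may need to be replaced to reach 20.
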